11. ADVERSE EVENTS

11.1

ADVERSE REACTIONS PREVIOUSLY

REPORTED

The study product has been reported to rarely produce skin irritation.

11.2 ADVERSE EXPERIENCES

An adverse experience is defined as any untoward medical occurrence (sign, symptom or laboratory finding), regardless of severity and whether or not attributed to the study product.

The investigator/coordinator will report all adverse experiences (AEs) that occur throughout the study. All AEs will be recorded in the appropriate AE log. The report will include: date of onset, a description of the AE, severity, seriousness, action taken, relationship to the study drug, outcome of the event, and date of resolution.

11.2.1 ASSESSMENT OF SEVERITY

The intensity or severity of an AE is characterized as:

Mild: AE which is easily tolerated.

Moderate: AE sufficiently discomforting to interfere with daily activity.

Severe: AE which prevents normal daily activities.

Subjects who are withdrawn from the study due to any AE will be followed by the investigator until the outcome is determined. The investigator will summarize and document all information relating to the AE and follow up.

11.2.2 RELATIONSHIP TO STUDY PRODUCT

The relationship is characterized as:

Not Related - applies to any adverse experience that is clearly not related to use of the study product.

Possible - means the association of the adverse experience with the study product is unknown; however, a relationship between study product and experience cannot be ruled out.

Probable - there is a reasonable temporal relationship between the use of the study product and the adverse experience. Based upon the investigator's clinical experience, the association of the event with the study product seems likely.

Definite - The AE occurs following the application of the study product and it cannot be reasonably explained by any other known characteristics of the subject's clinical state, environmental or toxic factors, or other modes of therapy administered to the subject. It disappears or decreases upon discontinuation of the study product and reappears on a re-challenge of the study product.

11.3 SERIOUS ADVERSE EVENTS

Definition: An SAE is defined as any adverse experience occurring that results in any of the following outcomes:

- 1. death
- 2. immediately life-threatening illness
- 3. hospitalization (> 24 hours) or prolongation of existing hospitalization
- 4. a persistent or significant disability
- 5. a congenital anomaly/birth defect
- 6. "other" important medical event

These are not anticipated, however, should an SAE occur, the primary investigator ([name]) will immediately notify the sponsor. The sponsor will provide instructions as to how to report the SAE to the FDA.

12. STATISTICAL METHODS

The statistical evaluation will be performed by Dermatology Consulting Services. Along with descriptive statistics (means, standard deviations and percentages), investigator and subject ordinal nonparametric data will be analyzed using the Wilcoxon signed rank test. Acne lesion counts will be assessed using a Student t test. Change will be considered significant at a p value of less than or equal to 0.05.

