- 10. Subjects who have a history of a psychological illness or condition that would interfere with their ability to understand and follow the requirements of the study.
- 11. Subjects who have undergone recent facial surgery.
- 12. Subjects currently participating in any other clinical trial.
- 13. Subjects having started hormone replacement therapies (HRT) or hormones for birth control less than 3 months prior to the study entry; or who plan on starting, stopping or changing doses of HRT or hormones for birth control during the study.
- 14. Subjects who have a cardiac pacemaker, implanted defibrillator, or other implanted metallic or electronic device.
- 15. Subjects who are wearing EKG monitoring equipment.
- 16. Subjects with phlebitis, thrombophlebitis, broken capillaries, or varicose veins.
- 17. Subjects who have seizures, epilepsy, or cancer/tumors.
- 18. Subjects who have a history of hypertrophic scarring or keloid formation.

Endpoints:

Tolerability Endpoint:

The tolerability endpoint is the investigator-assessed absence of skin irritation from the facial study device at any time during the 12-week study.

Safety Endpoint:

The safety endpoint is the overall incidence of all adverse events reported during the study.

Efficacy Endpoint: The efficacy endpoint is the investigator assessed improvement in investigator global assessment (IGA) after 12 weeks of every other day device use as compared to baseline.

Measures:

Dermatologist Investigator assessed efficacy parameters: Investigator global acne assessment (IGA) based on the following 5 point ordinal scale: 0=clear, 1=almost

clear, 2=mild, 3=moderate, and 4=severe. IGA assessments will be conducted at baseline, week 2, week 4, week 8, and week 12.

Dermatologist Investigator lesion counts: inflammatory lesion count (papules, pustules), non-inflammatory lesion count (open comedones, closed comedones). Lesion counts will be conducted at baseline, week 2, week 4, week 8, and week 12.

Dermatologist Investigator assessed tolerability parameters: peeling, dryness, redness, and swelling. All assessments will be made on a 5-point ordinal scale (0=none, 1=minimal, 2=mild, 3=moderate, & 4=severe) at baseline, week 2, week 4, week 8, and week 12.

Self-assessment questionnaire: To be provided by sponsor. All assessments will be at week 2, week 4, and week 8, and week 12.

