Subject assessed tolerability parameters: itching, burning, redness, and swelling. All assessments will be made on a 5-point ordinal scale (0=none, 1=minimal, 2=mild, 3=moderate, & 4=severe) at baseline, week 2, week 4, and week 8, and week 12.

Photography: all investigator selected subjects will be photographed with the Canfield VISIA CR using Standard 1 lighting at baseline, week 2, week 4, and week 8, and week 12.

Statistical Methods:

Along with descriptive statistics (means, standard deviations and percentages), investigator and subject ordinal nonparametric data will be analyzed using the Wilcoxon signed rank test. Acne lesion counts will be assessed using a Student t test. Change will be considered significant at a p value of less than or equal to 0.05.

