4. STUDY OBJECTIVE

The objective of this study is demonstrate the safety and efficacy of a novel direct current device in the treatment of mild to moderate inflammatory acne after 12 weeks of every other day use.

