5. STUDY DESIGN OVERVIEW

Male and female subjects will be enrolled in this single-site monadic study to evaluate the effect of a direct-current device on acne treatment. Subjects who sign the consent form and meet all inclusion criteria and none of the exclusion criteria will be enrolled at the baseline visit. Subjects will be asked to continue their self-selected moisturizer, non-medicated cleanser, and sunscreen they have used without difficulty for the prior 30 days and for the 12 week study. Subjects must also continue all facial products and cosmetics unchanged for the duration of the study. No other oral or topical acne products can be used. Subjects must be washed out of all topical acne products for at least 2 weeks and all oral acne products for at least 4 weeks. Subjects must possess mild to moderate acne with 5-30 inflammatory lesions and no nodules/cysts.

At baseline visit, subjects will receive the study acne device to be applied to the areas of the face afflicted by acne following cleansing, every other day. The dermatologist investigator will assess the face for the investigator global acne assessment (IGA) based on the following 5 point ordinal scale: 0=clear, 1=almost clear, 2=mild, 3=moderate, and 4=severe. In addition, the dermatologist investigator will perform an inflammatory and non-inflammatory lesion count. The dermatologist investigator will assess the tolerability of the device in terms of peeling, dryness, redness, and swelling on a 5-point ordinal scale (0=none, 1=minimal, 2=mild, 3=moderate, & 4=severe).

The subjects will assess device tolerability in terms of itching, burning, redness, and swelling. All assessments will be made on a 5-point ordinal scale (0=none, 1=minimal, 2=mild, 3=moderate, & 4=severe). Subjects will be given their diaries, study device, and electroconductive media and asked to return to the research center in 2 weeks. A reminder text will be sent to encourage compliance prior to the week 2 visit.

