12.1 SAMPLE SIZE RATIONALE

A sample size of 50 study subjects was chosen by the study sponsor.

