12.2 SIGNIFICANCE LEVEL

Significance is defined at the p<0.05 level based on a two-sided test.

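### The signed rank test planned for the tolerability grades measures net change, so worsening in some subjects can be offset by improvement in others; it does not estimate the stated endpoint of no irritation at any time

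*Combined protocol and SAP*

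**What the plan says.** Section 12 (repeated in the Synopsis under Statistical Methods) assigns one method to every ordinal outcome: "investigator and subject ordinal nonparametric data will be analyzed using the Wilcoxon signed rank test". Means, standard deviations and percentages are to accompany it, and change is judged at the 0.05 level. Section 12.2 adds: "Significance is defined at the p<0.05 level based on a two-sided test".

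The tolerability grades fall under that sentence. Section 5 has the investigator "assess the tolerability of the device in terms of peeling, dryness, redness, and swelling on a 5-point ordinal scale", and subjects grade "itching, burning, redness, and swelling" on the same 0-4 scale. Both sets are graded at baseline and at weeks 2, 4, 8 and 12. Redness and swelling are on both lists, so they make up four of the eight grades.

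The tolerability endpoint is defined in the Synopsis (Endpoints) and in section 12.3. It is met when the investigator finds no skin irritation from the device at any point over the 12 weeks. No section says how the grades feed into that endpoint or how the endpoint is to be analysed.

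The objective in section 4 concerns "treatment of mild to moderate inflammatory acne", and section 6.3 requires 5 to 30 inflammatory lesions at entry. Section 10.6 confirms that all subjects use the active device.

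**The concern.** The endpoint and the test answer different questions. The endpoint is a yes/no outcome for each subject over all visits. The signed rank test compares the rank-weighted rises with the rank-weighted falls across subjects, for whatever pair of visits is analysed. A subject whose grade falls counts against a subject whose grade rises, although nobody's irritation has gone away.

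This is true of all eight grades. It matters most for redness and swelling. Subjects enter with papules and pustules, so some baseline redness or swelling may come from the acne and may fall as the acne clears. The grading text has no rule for separating lesion redness from device irritation, and there is no control arm to separate them afterwards.

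Safety is a co-objective of the trial. At stake is a tolerability statement of no significant change, or even of significant improvement, in a sample where a material share of subjects became worse. The more effective the device, the stronger the offset could be.

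**Working it through.** **Inputs from the protocol.** n = 50 (section 12.1: "A sample size of 50 study subjects was chosen by the study sponsor"); two-sided 0.05 (section 12.2); one arm; 0-4 grades. The sample size comes with no effect size, SD or power, so there is no stated calculation to reproduce.

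**Inputs assumed.** The protocol gives no expected rate of worsening or improvement. I fix 10 of 50 worsening, vary the number improving, and assume no dropout.

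**One-grade changes, exact test.** If every non-zero change is one grade, all ranks are tied and the exact signed rank test reduces to a sign test. With w worsening and i improving, p = min(1, 2 × P(X ≥ max(w, i))), where X ~ Binomial(w + i, ½). For w = 10, i = 0: p = 2 × (½)^10 = 2/1024 = 0.002.

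| Worsen | Improve | Mean change | Exact p | Direction |
|---|---|---|---|---|
| 10 | 0 | +0.20 | 0.002 | worse |
| 10 | 2 | +0.16 | 0.039 | worse |
| 10 | 3 | +0.14 | 0.092 | not significant |
| 10 | 10 | 0 | 1.0 | none |
| 10 | 20 | -0.20 | 0.099 | not significant |
| 10 | 25 | -0.30 | 0.017 | improvement |

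The normal approximation, z = (w - i)/√(w + i), gives the same picture. For 10 vs 20, z = -10/√30 = -1.83 and p = 0.068. For 10 vs 25, z = -15/√35 = -2.54 and p = 0.011.

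**Two-grade worsening.** Here the offset is only partial, because larger changes carry larger ranks. Take 10 subjects up two grades and 20 down one.
- The 20 falls share rank 10.5 and the 10 rises share rank 25.5.
- The signed sum is 10 × 25.5 - 20 × 10.5 = 45.
- Its standard deviation is √(10 × 25.5² + 20 × 10.5²) = √8707.5 = 93.3.
- So z = 0.48 and p = 0.63, with mean change 0.

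With 10 improvers instead of 20, p = 0.054. Even with all 40 other subjects improving by one grade, p = 0.060, so a significant improvement does not appear.

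**Range of rates.** Simulation used 5,000 trials per cell, n = 50, one-grade changes and the normal approximation. Entries are the chance of a significant worsening.

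| True worsening rate | 0% improve | 10% | 20% | 30% |
|---|---|---|---|---|
| 10% | 76% | 2.7% | 0% | 0% |
| 20% | 99% | 24% | 2.8% | 0.3% |
| 30% | 100% | 64% | 18% | 2.4% |

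At 20% worsening and 50% improving, the test shows a significant improvement in 75% of trials.

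**The per-subject count.** 10/50 = 20%, with exact (Clopper-Pearson) 95% CI 10.0% to 33.7%, whatever the other 40 subjects do. For 5/50 the interval is 3.3% to 21.8%; for 15/50 it is 17.9% to 44.6%. For 0/50 the upper limit is 7.1%.

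**Baseline order.** Section 7.2.1 describes a supervised first use of the device at the baseline visit, and then the tolerability grading, without fixing the sequence. If baseline is graded after that use, immediate redness becomes part of the reference value and later rises look smaller.

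**The case against.** The strongest reply is that the plan's tolerability endpoint is already per-subject and any-time, so it cannot be netted across subjects; on this view the signed rank test only supports it. The endpoint is also investigator-assessed, so the subject-rated grades do not enter it. Other reporting routes are not offset either. Section 11.2 records every untoward occurrence whatever its severity, section 12.4 tabulates adverse events by relationship, section 9.1 codes discontinuation for contact dermatitis, and section 12.3 queries those who stop. Percentages are planned as well.

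Much of this stands, and it limits the point. A reader might infer that irritation would vanish from the report as a whole. The documents do not support that: the offset affects the test results and mean changes, not the adverse event tables. The protection is still partial. Percentages by grade and visit do not show who rose above their own baseline, no rule turns a rise in grade into an adverse event, and the only analysis named for the grades is the net-change test.

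A reader might also infer that every subject has redness and swelling from acne at baseline, so that irritation will be cancelled. No section says this. The grades are described as device tolerability, and a subject with five papules may be graded 0. A subject at 0 cannot improve and so offsets nobody. For 20 or 25 subjects to improve, 40% or 50% must start above 0 and then fall, and the protocol gives neither rate.

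**Conclusion.** The point holds as a mismatch between test and endpoint. Worsening can be offset by improvement; the documents do not show that it will be. By construction this applies to all eight grades. The route through acne clearing is most plausible for redness and swelling, and it rests on an inference from the inflammatory nature of the disease.

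The size depends on assumed rates. With 10 of 50 subjects worsening by one grade, three improvers are enough to remove significance, and 25 produce a significant improvement. With two-grade worsening, the cases computed lose significance from 10 improvers on but do not reverse it. The small difference between the 0.05 rule in section 12 and that in section 12.2 does not affect any of these results. The point merits a change to the analysis because the data needed for a better-matched summary are already being collected.

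**What to change.** - For each of the eight grades, report the number and percentage of subjects whose worst post-baseline grade exceeds their own baseline, with an exact 95% CI and a shift table of baseline against worst grade.
- Report the same count overall for the investigator-assessed grades (a rise in any of the four). Name this as the analysis that supports the tolerability conclusion in section 12.3.
- Keep the signed rank test for the tolerability grades as descriptive only.
- State in section 7.2.1 that baseline tolerability is graded before the first device use.

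I would not add an instruction to grade redness and swelling only on skin between lesions. Section 10.3 has subjects move the probe over the acne itself, so such a rule would leave irritation at the treated sites ungraded.

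The cost is some analysis wording and one sentence on the order of procedures, with no extra visits, subjects or data items. The downside is a higher reported rate. It counts any rise at any of four post-baseline visits, and with no control arm it will include some acne flares scored as redness or swelling. The report should say so beside the figure.

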12.1 SAMPLE SIZE RATIONALE

A sample size of 50 study subjects was chosen by the study sponsor.

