7.1.5 STUDY MATERIAL ADMINISTRATION

All subjects will use the active ZIIP device as currently marketed. The ZIIP Device will be customized for the delivery of acne treatment with -400 microamps direct current, applied 3 days per week on non-consecutive days, on each facial zone afflicted by acne. A electroconductive media will be applied to each facial zone afflicted by acne prior to initiation of the device treatment.

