12.4 SAFETY ASSESSMENT

Incidence of all adverse events reported during the study will be summarized. Tabulated summaries will include adverse events grouped by relation to study product. The safety endpoint is the absence of significant adverse reactions.

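### A zero-count safety endpoint in 50 subjects, with no interval planned, excludes only reaction rates above 7.1%, and the synopsis states a different safety endpoint

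*Combined protocol and SAP*

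**What the plan says.** The combined protocol and SAP describes safety in several places that do not fit together.

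- Section 4 (Study Objective): "The objective of this study is demonstrate the safety and efficacy of a novel direct current device".
- Section 1 (Protocol Synopsis, Endpoints): "The safety endpoint is the overall incidence of all adverse events reported during the study". This is descriptive and has no pass or fail condition.
- Section 12.4 (Safety Assessment) opens in the same way: "Incidence of all adverse events reported during the study will be summarized". Tables are to be grouped by relation to the study product. It then closes with a criterion: "The safety endpoint is the absence of significant adverse reactions".
- Section 12.1 (Sample Size Rationale) is one sentence: "A sample size of 50 study subjects was chosen by the study sponsor". It gives no rate, margin, power or precision target.
- Section 12 lists descriptive statistics and two tests. Neither it nor 12.4 plans a confidence interval.

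No section defines a significant adverse reaction. Section 11 grades events as mild, moderate or severe, classifies their relationship to the product, and defines serious events, but 12.4 refers to none of these categories. The cover page names a historical control, but no historical adverse event rate is given.

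**The concern.** Seeing no events is not the same as showing that the event rate is low. Section 12.4 treats a zero count as the safety endpoint and the objective is worded as a demonstration, yet nothing in the plan turns that count into a statement about the device's true rate. A reader told that none of 50 subjects had a significant reaction would not learn which rates remain possible.

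The criterion is also fragile in the other direction. A single event fails it, however low the true rate, and no acceptable rate is given against which to interpret one event. Finally, because the synopsis and 12.4 differ, the same data could meet one safety endpoint, fail it, or simply be described under the other.

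**Working it through.** **Inputs**

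- n = 50, one arm (sections 6.1 and 12.1). Every subject is exposed: "All subjects will use the active ZIIP device as currently marketed" (7.1.5).
- Criterion: zero subjects with a significant adverse reaction (12.4, read literally).
- Confidence level: two-sided 95%, to match the only convention stated, "Significance is defined at the p<0.05 level based on a two-sided test" (12.2). That section does not link it to safety.
- True rate p: not in the documents. Section 11.1 says only "The study product has been reported to rarely produce skin irritation". The values of p below are therefore assumptions, shown as a range.

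**The plan's own figure.** The 50 cannot be reproduced, because no input is given from which to derive it.

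**Step 1: chance of meeting the criterion.** With independent subjects, P(no events) = (1 − p)^50.

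| True rate p | Meets criterion | Fails criterion |
|---|---|---|
| 0.5% | 77.8% | 22.2% |
| 1% | 60.5% | 39.5% |
| 2% | 36.4% | 63.6% |
| 3% | 21.8% | 78.2% |
| 5% | 7.7% | 92.3% |
| 8% | 1.5% | 98.5% |

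The chance is even at p = 1 − 0.5^(1/50) = 1.4%.

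**Step 2: what 0/50 excludes.** The exact (Clopper-Pearson) upper limit with no events is 1 − a^(1/n).

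- Two-sided 95%: 1 − 0.025^(1/50) = 7.1%.
- One-sided 95%: 1 − 0.05^(1/50) = 5.8%.

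**Step 3: what one event would mean.** The exact two-sided 95% interval for 1/50 is 0.05% to 10.6%. It overlaps heavily with the 0% to 7.1% interval for 0/50, yet the criterion gives the two results opposite labels.

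**Step 4: sensitivity to lost safety data.** No dropout rate is stated. If, as an assumption, only 45 or 40 subjects contributed safety data, the two-sided limit with no events would be 1 − 0.025^(1/45) = 7.9% or 1 − 0.025^(1/40) = 8.8%.

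**The case against.** The strongest reply is that 12.4 need not be read as a formal test. The synopsis endpoint is descriptive, 12.4 itself begins with a summary of incidence, and no sentence says that a zero count triggers a declaration of safety. The limit in step 2 also applies to any study of 50 subjects, and a small single-arm study may be sized on practical grounds. All of this is fair. It means that the size of 50 is not itself the error, and that a formal declaration is an inference from the objective read together with the last sentence of 12.4. It does not remove the conflict between the two endpoints, the undefined event, or the lack of an interval under either wording.

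A reader might go further in three ways that the documents do not support.

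- That a device with a reaction rate of several percent would pass. Step 1 shows that it could, but from 2% upward it fails more often than it passes.
- That the study cannot demonstrate safety. This needs a benchmark, and none is given. For some kinds of reaction, excluding rates above 7.1% might be adequate; for others it would not.
- That dropout makes 8.8% the realistic limit. Discontinuing subjects are asked about side effects (12.3), those withdrawn for an adverse event are followed (11.2.1), and a termination form is completed for everyone who receives product (section 9). The first device use also takes place at the site at baseline (7.2.1). The step 4 figures apply only if the missing subjects contribute no safety data at all.

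**Conclusion.** The point holds in a limited form. The plan states two different safety endpoints, and the one in 12.4 is a zero-count criterion for an undefined event with no interval and no acceptable rate. Followed as written, it would let a clean result be read as stronger than 50 subjects support: 0/50 leaves every rate up to 7.1% compatible with the data. It would also fail a device with a 1% rate 39.5% of the time.

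The figures assume independent subjects, one count per subject, absence read as zero events, and all 50 subjects in the denominator. Whether a 7.1% limit is good enough depends on a definition and a threshold that the documents do not give, so no judgement is made here on whether 50 is too few.

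The collected data are unaffected. What changes is the conclusion that may be drawn from them, so the change should be made before the safety results are reported.

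**What to change.** 1. Reconcile the synopsis and 12.4 into one safety endpoint, worded identically in both places.
2. Define a significant adverse reaction before analysis. The sponsor and investigator could do this with the severity, relationship and seriousness categories already in section 11.
3. In 12.4, report the proportion of subjects with each adverse event, and with any significant adverse reaction, each with an exact (Clopper-Pearson) two-sided 95% confidence interval. Use all subjects who receive the device as the denominator.
4. Replace the zero count as the safety conclusion with the estimate and its upper limit.
5. In 12.1, state the precision that the size provides: no events in 50 subjects excludes only rates above 7.1% (exact two-sided 95%).

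The cost is a wording amendment and slightly more table work. The safety claim becomes weaker, because it becomes an upper limit instead of an absence. No subjects, visits or procedures are added.
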